11.0 Safety Analysis

11.1 General Considerations

Safety analyses will include adverse events, laboratory, local tolerability, and vital sign measurements.

For the safety analyses, a baseline value (BL_RZB) is defined as the last non-missing observation on or prior to the date of the first dose of Risankizumab either in Study M15-997 or the preceding studies whichever is the earlier.

For subjects from Japan among the RZB, RZB_NL, Retreatment and UST_RZB Populations, only data prior to the start of risankizumab 75 mg dose will be used in the safety analyses. This subgroup analysis will only be performed in the final analysis, upon study completion.

When summarizing the safety for risankizumab 150 mg among the ALL_RZB Population, safety data collected (i) from feeder studies not using risankizumab 150 mg dose and/or (ii) from subjects in Japan who have started the risankizumab 75 mg dose will not be included for the safety summary of risankizumab 150 mg dose.

For the RZB Japan Population, safety data will be summarized regardless of dose.

Summaries of treatment-emergent adverse events (TEAEs), potentially clinically important laboratory values and vital sign values, and liver function tests will be provided for all populations. Analysis of change from baseline in laboratory values and vital sign values, shift tables and local tolerability will be provided for RZB, RZB_NL, UST_RZB, ADA_RZB, FUM_RZB, RZB Japan populations.

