To assess the benefit-risk profile, safety summaries will be provided for each of the above analysis populations as well. In addition, an All Risankizumab Treated Population, defined as all subjects who received at least one dose of risankizumab in this study, will be used to provide a comprehensive summary of safety.

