8.1.5 Safety Analysis

All AEs, SAEs, AEs leading to discontinuation, and pre-specified AESIs will be collected during the study. A treatment-emergent AE (TEAE) is defined as an event with onset or worsening after the first study dose of a risankizumab (either in a preceding Phase 2/3 psoriasis study or this study) and within 20 weeks (140 days) after the last study drug injection. The number and percentages of subjects experiencing TEAE will be tabulated using the Medical Dictionary for Drug Regulatory Activities (MedDRA[®]) system organ class and preferred term. Summaries (including percentages and event per 100 patient-years) of SAEs, deaths, AEs leading to discontinuation from the study, and pre-specified AESIs will be provided as well. Mean change in laboratory and vital signs variables will be summarized. For selected parameters, a listing of all subjects with clinically significant laboratory or vital sign values will be provided. Shift tables for changes from baseline according to the normal range will also be provided.

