5.1 Definition for Analysis Populations

RZB Population:

The RZB population consists of subjects who were randomized to risankizumab 150 mg in Studies 1311.3, 1311.30, 1311.28, 1311.38, and M16-178. This population will be used to evaluate the long-term safety and efficacy of risankizumab 150 mg with loading dose. For subjects from Japan, data after the first dose of risankizumab 150 mg from the preceding studies, and prior to the start of 75 mg dose will be used for the analyses.

RZB_NL Population:

The RZB_NL population consists of subjects who were randomized to placebo in the initial study and switched to risankizumab 150 mg (without loading dose) in Studies 1311.3, 1311.4, 1311.28, and 1311.38. This population will be used to evaluate the long-term safety and efficacy of risankizumab 150 mg without initial loading dose. For subjects from Japan, data after the first dose of risankizumab 150 mg from the preceding studies, and prior to the start of 75 mg dose will be used for the analyses.

Retreatment Population:

The Retreatment population consists of subjects who were re-randomized to placebo in Part B of Study 1311.4 and received retreatment of risankizumab 150 mg. This population will be used to evaluate the safety and efficacy of re-treatment after temporary withdrawal. For subjects from Japan, data after the re-treatment and prior to the start of 75 mg dose will be used for the analyses.

UST_RZB Population:

The UST_RZB population consists of subjects who were randomized to ustekinumab in Studies 1311.3 and 1311.28. This population will be used to assess the safety and efficacy of risankizumab 150 mg when subjects switch from ustekinumab to risankizumab

150 mg. For subjects from Japan, data prior to the start of 75 mg dose will be used for the analyses.

ADA RZB Population:

The ADA_RZB population consists of subjects who were randomized to adalimumab in Study 1311.30 and switched to risankizumab. This population will be used to assess the safety and efficacy of risankizumab when subjects from adalimumab to risankizumab.

FUM RZB Population:

The FUM_RZB Population consists of subjects who were randomized to Fumaderm[®] (fumaric acid esters) in Study M16-178. This population will be used to assess the safety and efficacy of risankizumab when subjects switch from Fumaderm[®] to risankizumab.

RZB Japan Population:

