11.3.2 Statistical Methods

Analysis of Quantitative Laboratory Parameters (Hematology, Chemistry)

Though the protocol indicates utilizing the Rheumatology Common Toxicity Criteria (RCTC) scale for grading laboratory values, given that the National Cancer Institute Common Toxicity Criteria for Adverse Events (NCI CTCAE) scale includes a more comprehensive list of laboratory values, the sponsor will present the lab analyses based on the NCI CTCAE scale. Changes from Baseline to each scheduled visit and to the final value in continuous laboratory parameters will be summarized with the mean, standard deviation and median. The Baseline (BL_RZB) and visit/final value means will also be presented for subjects who have both the Baseline and visit/final values. If there are multiple post-baseline measurements on the same day, average value will be used.

Shift Tables

Laboratory parameters will be tabulated using shift tables from Baseline to worst values, categorized by the toxicity grade according to NCI CTCAE Version 4.03 of the laboratory used for each sample. A similar shift table will also be provided to summarize shifts from Baseline to the final post-baseline value.

Potentially Clinically Important Laboratory Values

Frequencies and percentages of subjects with post Baseline lab values met the following criteria in [Table 14](#) and [Table 15](#) will be summarized. Of note, a post baseline grade must be more extreme than the baseline grade to be considered a potentially clinically important finding.

Table 14. Criteria for Potentially Clinically Important Chemistry Values

Chemistry Variables	Units	Definition of Potentially Clinically Important Current (Version 4) NCI CTCAE Grade 3 or Greater	
		Very Low	Very High
TBL	mcmol/L		> 3.0 × ULN
SGOT/AST	U/L		> 5.0 × ULN
SGPT/ALT	U/L		> 5.0 × ULN
Albumin	g/L	< 20	
Glucose	mmol/L	< 2.2	> 13.9
Triglycerides	mmol/L		> 5.7
Creatinine	mcmol/L		> 3.0 × ULN (> 3.0 × BL)
Sodium	mmol/L	< 130	> 155
Potassium	mmol/L	< 3.0	> 6.0
Calcium	mmol/L	< 1.75	> 3.1
CPK	U/L		> 5.0 × ULN
Total Cholesterol	mmol/L		> 10.34
GGT			> 5.0 × ULN
ALP			> 5.0 × ULN

Table 15. Criteria for Potentially Clinically Important Hematology Values

Hematology Variables	Units	Definition of Potentially Clinically Important Current (Version 4) Grade 3 or Greater
		Very Low
Hemoglobin	g/dL	< 8.0
Platelets count	10 ⁹ /L	< 50.0
WBC count	10 ⁹ /L	< 2.0
Neutrophils	10 ⁹ /L	< 1.0
Lymphocytes	10 ⁹ /L	< 0.5

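### SAP 11.1 leaves ALL_RZB and Retreatment out of the change, laboratory shift and local tolerability outputs, so some subjects appear in none of them; separately, the protocol's normal-range shifts are not planned

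*SAP*

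**What the plan says.** **Coverage.** SAP 11.1 divides the safety outputs into two sets. The first is for everyone: treatment-emergent adverse events, and "potentially clinically important laboratory values and vital sign values, and liver function tests will be provided for all populations". The second covers change from baseline in laboratory and vital-sign values, together with the following: "shift tables and local tolerability will be provided for RZB, RZB_NL, UST_RZB, ADA_RZB, FUM_RZB, RZB Japan populations". ALL_RZB and Retreatment are in the first set only.

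Protocol 8.1.1 says that safety summaries will be given for each of its listed analysis populations, and Retreatment is one of them. It adds an All Risankizumab Treated Population that "will be used to provide a comprehensive summary of safety". Safety and tolerability are the primary objective (Protocol 4.0).

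**Basis of the shift tables.** Protocol 8.1.5: "Shift tables for changes from baseline according to the normal range will also be provided". SAP 11.3.2 plans "shift tables from Baseline to worst values, categorized by the toxicity grade according to NCI CTCAE Version 4.03", and a similar table to the final value. It explains why CTCAE replaces the RCTC scale for grading, but does not mention the normal-range shifts. SAP 14.1, the place for differences between protocol and SAP, has no entry.

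**The concern.** There are two separate points.

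First, the six populations in SAP 11.1 do not add up to the treated population. Each is built from particular feeder studies and arms, and only ALL_RZB takes in everyone. With ALL_RZB left out, any subject who belongs to no other listed population drops out of the change, laboratory shift and local tolerability outputs. In a long-term extension those are the summaries that would show a gradual drift in a laboratory value or blood pressure that never crosses a severe threshold. Leaving out Retreatment also removes most of the laboratory description for the group in which drug was withdrawn and restarted. Protocol 8.1 names the safety of those subjects as an additional objective.

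Second, the protocol commits to one kind of shift table and the SAP delivers another without recording the departure. A CTCAE-grade shift and a low/normal/high shift answer different questions, and readers of the protocol will expect the latter.

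**Working it through.** No formula applies to the coverage point. The check is to place each feeder group in the SAP 5.1 populations and compare the result with the SAP 11.1 list.

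**Definitions used (SAP 5.1).** RZB takes subjects "randomized to risankizumab 150 mg in Studies 1311.3, 1311.30, 1311.28, 1311.38, and M16-178", so neither 1311.4 nor 1311.13. RZB_NL takes only subjects "randomized to placebo in the initial study and switched to risankizumab 150 mg (without loading dose) in Studies 1311.3, 1311.4, 1311.28, and 1311.38". Retreatment takes those "re-randomized to placebo in Part B of Study 1311.4 and received retreatment of risankizumab 150 mg". UST_RZB, ADA_RZB and FUM_RZB are the comparator arms of 1311.3 and 1311.28, of 1311.30, and of M16-178. RZB Japan is every subject from Japan during the extension, at any dose, analysed only at study completion.

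| Feeder group | Populations under SAP 5.1 | In the SAP 11.1 change/shift list? |
|---|---|---|
| Randomised to 150 mg in 1311.3, 1311.28, 1311.30, 1311.38, M16-178 | RZB, ALL_RZB | Yes |
| Initial placebo, switched to 150 mg, in 1311.3, 1311.4, 1311.28, 1311.38 | RZB_NL, ALL_RZB | Yes |
| Ustekinumab, adalimumab, Fumaderm arms | UST_RZB, ADA_RZB or FUM_RZB; ALL_RZB | Yes |
| 1311.38, 75 mg | RZB Japan, ALL_RZB (taking 1311.38 as the Japanese study that Protocol 5.6.4 describes) | Yes, final analysis only |
| 1311.13, not Japan | ALL_RZB only | **No** |
| 1311.4, risankizumab, not re-randomised to placebo, not Japan | ALL_RZB only | **No** |
| 1311.4, risankizumab, re-randomised to placebo and retreated, not Japan | Retreatment, ALL_RZB | **No** |

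Any subject from Japan in the last three rows is picked up through RZB Japan, but only in the final analysis.

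**Size.** Protocol 5.6.4 gives 110 subjects enrolled in 1311.13. SAP 4.3 gives about 2200 expected in the extension.
- Upper bound: 110 / 2200 = 5.0%.
- If the 10% to 15% dropout in SAP 4.3 is assumed to apply to 1311.13: 110 × 0.90 = 99 (4.5%) and 110 × 0.85 = 93.5, about 94 (4.3%).
- The documents give no number for 1311.4 or its arms, so that part cannot be sized.

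**Would the change close the gap?** Adding ALL_RZB puts every row in at least one table. Adding Retreatment alone recovers only the last row; the two rows above it stay uncovered. Both are therefore needed, the first for completeness and the second for Protocol 8.1.1.

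**Are visit windows an obstacle?** SAP Tables 5 to 7 give Retreatment windows for efficacy variables only, and there are none for ALL_RZB. Baseline-to-worst and baseline-to-final summaries need none, because SAP 6.0 already defines a baseline for safety in all populations (BL_RZB) and a final observation (within 140 days of the last risankizumab dose).

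**Basis of the shift.** Protocol 8.1.5 and SAP 11.3.2 use different categories: normal range against CTCAE grade. SAP 11.3.2's explanation concerns two toxicity scales, RCTC and CTCAE, and neither is a normal-range classification. So no normal-range shift is planned for any test, and no reason is given.

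**The case against.** The strongest case against is that this is a legitimate choice of scope. Protocol 8.1.1 promises safety summaries per population, not every output for every population. Protocol 8.1.5 attaches no population to the shift tables, and Protocol 8.1 leaves detail to the SAP. The uncovered subjects do have laboratory review: potentially clinically important values and liver tests for all populations (SAP 11.1), and a listing of every subject with a grade 3 or higher value with the whole course of that parameter (SAP 11.3.2). SAP 11.3 also plans summaries of the value furthest from the reference range. The study is descriptive, with no tests.

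Much of this stands, and it limits the harm. It does not remove the point. The laboratory criteria in SAP Tables 14 and 15 are set at grade 3 or greater, and the liver categories cover four analytes. Neither summarises change from baseline or movement between lower grades. SAP 11.3 names no population, so SAP 11.1 governs who is included. No reason for the restriction is stated.

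Several stronger readings are tempting but not supported:
- That the move to CTCAE grades causes the coverage gap. It removes no subject from any table.
- That no withdrawal or retreatment subject has a shift analysis. The SAP 5.1 Retreatment definition shows that 1311.4 had subjects from Japan, and RZB Japan receives these outputs at the final analysis.
- That vital-sign shift tables are being withheld. SAP 11.4 plans none for any population; for vital signs the gap is in the change summaries.
- That a total percentage uncovered can be stated. It would rest on an assumed size for 1311.4.
- That tests without a threshold in Tables 14 and 15 lose more than the others. Those tables do not decide which tests enter the shift tables, and no test has a normal-range shift.

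**Conclusion.** Both points hold, within limits.

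1. Subjects not from Japan who came from 1311.13, or who were initially randomised to risankizumab in 1311.4, are in no planned laboratory or vital-sign change summary, laboratory shift table or local tolerability summary. The size is at most 110 of about 2200 (5.0%) for 1311.13, plus an unstated number from 1311.4. For these subjects the plan falls short of a comprehensive safety summary; it does not leave them without safety data. At the second interim analysis RZB Japan is not analysed, so subjects from Japan in the same feeder groups would be missing from these outputs there as well.

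2. The SAP departs from the protocol on the basis of the shift tables without saying so.

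The conclusion rests on reading the SAP 11.1 list as exhaustive, on the SAP 5.1 definitions as written, and on 1311.38 being conducted in Japan.

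**What to change.** **Coverage (SAP 11.1).** Add ALL_RZB (any dose) and Retreatment to the baseline-to-worst and baseline-to-final laboratory shift tables, to the baseline-to-final change summaries for laboratory and vital-sign values, and to the local tolerability summary. The any-dose version is the cleaner one: SAP 11.1 excludes feeder data at other doses from the 150 mg summary, yet for 1311.13 subjects, who were treated at 90 mg with an option of 180 mg, BL_RZB precedes those doses.

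Three data-handling statements are needed, because the existing rules do not cover these tables:
- The treatment-gap exclusion in SAP 11.2.1 is written only for adverse events. Apply it to laboratory and vital-sign values too: in ALL_RZB, leave out values from the 1311.4 Part B placebo period taken more than 140 days after the last prior risankizumab dose and before retreatment. Otherwise the worst value may come from time off drug.
- For Retreatment, use only post-baseline values after the first retreatment dose.
- State that BL_RZB is the value before the first-ever risankizumab dose, so a Retreatment shift is measured from there and not from the start of retreatment.

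**Normal-range shifts (SAP 11.3.2).** Add low/normal/high shift tables for the quantitative tests in SAP Table 13, alongside the CTCAE-grade tables. This restores what Protocol 8.1.5 specifies.

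**Cost.** A few extra tables, largely from existing programs, and a short data-handling paragraph. No new data collection and no change to the conduct of the study.

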11.2 Analysis of Adverse Events

11.2.1 Treatment-Emergent Adverse Events

Treatment emergent adverse events (TEAEs) are defined as any event with an onset date that is after the first dose of risankizumab and with an onset date within 140 days after the last dose of study drug in the analysis period except:

- **TEAE of Retreatment:** TEAE are defined as any event with an onset date that is after the first dose of retreatment and no more than 140 days after the last dose of study drug, and prior to the start of risankizumab 75 mg (if any, for subjects in Japan).
- **TEAE of ALL_RZB (any dose):** TEAEs are defined as any event with an onset date after the first dose of risankizumab through 140 days after the last dose of risankizumab, except for AEs with an onset date during protocol-designed treatment gaps (i.e., placebo period in subjects re-randomized to placebo during Study 1311.4 Part B) that was more than 140 days from the last dose of previous risankizumab treatment and before the first dose of retreatment in the ALL_RZB Population.
- **TEAE of RZB, RZB_NL, UST_RZB, ADA_RZB, FUM_RZB and ALL_RZB (150 mg):** TEAEs are defined as any event with an onset date after the first dose of risankizumab 150 mg through 140 days after the last dose of risankizumab 150 mg, and prior to the start of risankizumab 75 mg (if any, for subjects in Japan), except for AEs with an onset date during protocol-designed treatment gaps (i.e., placebo period in subjects re-randomized to placebo during Study 1311.4 Part B) that was more than 140 days from the last dose of

previous risankizumab 150 mg treatment and before the first dose of retreatment in the ALL_RZB Population.

Events where the onset date is the same as the study drug start date are assumed to be treatment emergent, unless the adverse event start time is prior to the study drug start time. If an incomplete onset date is collected for an adverse event, the event will be assumed to be treatment-emergent unless there is other evidence that confirms that the event is not treatment-emergent (e.g., the event end date is prior to the study drug start date).

The number and percent of subjects experiencing treatment-emergent TEAEs will be tabulated using the Medical Dictionary for Drug Regulatory Activities (MedDRA[®]) system organ class and preferred term.

Summary tables will be presented as follows:

1. Adverse Event Overview

The number and percentage of subjects experiencing treatment-emergent adverse events will be summarized for the following adverse event categories:

- Any AE
- Any AE that was assessed as related to study drug by the investigator
- Any severe AE
- Any serious AE
- Any serious AE that was assessed as related to study drug by the investigator
- Any AE leading to discontinuation of study drug
- Any AE leading to death
- Any deaths
- Areas of Safety Interest
- Any COVID-19 Related AE

2. Adverse Events by System Organ Class and Preferred Term

TEAEs will also be summarized and presented using primary Medical Dictionary for Regulatory Activities (MedDRA) system organ classes (SOCs) and preferred terms (PTs). The SOCs will be presented in alphabetical order, and the PTs will be presented in alphabetical order within each SOC.

Subjects reporting more than one adverse event for a given MedDRA preferred term will be counted only once for that term (most severe incident for the severity tables and most related incident for the relationship tables). Subjects reporting more than one type of adverse event within a SOC will be counted only once for that SOC. Subjects reporting more than one type of adverse event will be counted only once in the overall total.

In addition, the number and percentage of adverse events with causal relationship between the events and the study drug will be summarized using the same conventions described above.

3. Adverse Events by Maximum Severity

The severity grading of AEs follows Rheumatology Common Toxicity Criteria (RCTC).

- Grade 1 – mild
- Grade 2 – moderate
- Grade 3 – severe
- Grade 4 – life threatening

Adverse events will also be summarized by maximum severity. If a subject has an adverse event with unknown severity, then the subject will be counted in the severity category of "unknown," even if the subject has another occurrence of the same event with a severity present. The only exception is if the subject has another occurrence of the same adverse event with the most extreme severity – ("Life-threatening"). In this case, the subject will be counted under the "Life-threatening" category.

4. Adverse Events by Maximum Relationship

Adverse events will be summarized by maximum relationship to study drug, as assessed by the investigator. Relationship of an AE to study drug is assessed by the investigator and collected in the CRF as 'Yes' or 'No.' If a subject has an adverse event with unknown relationship, the subject will be counted in the relationship category of "unknown," even if the subject has another occurrence of the same event with a relationship of "No." If the subject has another occurrence of the same adverse event with a relationship assessment of "Yes," the subject will be counted under the "yes" category.

A listing of all pretreatment (i.e., events start prior to the first study drug injection) serious adverse events will be provided.

The following tables are planned.

Treatment-emergent adverse events will be summarized as follows:

- Grouped by System Organ Class and Preferred Term
- Grouped by System Organ Class, Preferred Term and Maximum Relationship to Study Drug
- Grouped by System Organ Class, Preferred Term and Maximum Severity

Treatment-emergent serious adverse events will be summarized as follows:

- Grouped by System Organ Class and Preferred Term
- A by-subject listing will be provided

Pre-treatment serious adverse events will be summarized as follows:

- A by-subject listing will be provided

Treatment-emergent adverse events leading to death or premature discontinuation of study drug will be summarized as follows:

- Grouped by System Organ Class and Preferred Term
- Separate listings by subject for deaths and premature terminations of study drug due to adverse events will be provided.

Treatment-emergent areas of safety interest will be summarized as follows:

- Grouped by System Organ Class and Preferred Term
- A listing by subject will be provided.

Areas of Safety Interest:

Areas of Safety Interest (ASIs) will be summarized according to the search criteria provided in [Table 12](#).

The final list will be based on the most updated final version of risankizumab Product Safety Statistical Analysis Plan, which is consistent to the most updated risankizumab Risk Management Plan.

Table 12. Areas of Safety Interest

Area of Safety Interest	Search Criteria	
MACE	Adjudicated terms will be identified as described in PSSAP Table 4a using CECAT and CETERM from the CE SDTM dataset.	
Extended MACE	Adjudicated terms will be identified as described in PSSAP Table 4a (for MACE +) using CECAT and CETERM from the CE SDTM dataset.	
Serious Infections	Serious AEs in the Infections and Infestations SOC	
Active Tuberculosis	Active Tuberculosis CMQ (code 80000188)	
Opportunistic Infections excluding tuberculosis and herpes zoster	Opportunistic infection excluding tuberculosis and herpes zoster CMQ (code 80000189)	
Injection Site Reactions	Narrow	Injection site reaction CMQ (code 80000019)
Malignancies	Narrow	Malignant tumours (SMQ 20000194)
Non-melanoma Skin Cancer (NMSC)	Broad	Skin malignant tumours (SMQ 20000204) excluding terms identified by the Melanoma CMQ (code 80000119)
Malignant Tumours excluding NMSC	'Malignant Tumours excluding NMSC' is identified by the 'Malignant Tumours' search excluding terms identified by the 'Non-melanoma skin cancer (NMSC)' search.	
Hypersensitivity	Narrow	Hypersensitivity (SMQ 20000214)
Serious hypersensitivity reactions	Narrow	Serious AEs in the Hypersensitivity (SMQ 20000214)
Adjudicated Anaphylactic Reaction*	Adjudicated terms will be identified using SDTM data (e.g., CE and PR domains).	
Hepatic Events	Broad	Hepatic failure, fibrosis and cirrhosis and other liver damage-related conditions (SMQ 20000013)
	Broad	Hepatitis, non-infectious (SMQ 20000010)
	Broad	Cholestasis and jaundice of hepatic origin (SMQ 20000009)
	Broad	Liver related investigations, signs and symptoms (SMQ 20000008)
	Narrow	Liver-related coagulation and bleeding disturbances (SMQ 20000015)

* Events will be identified for adjudication by Anaphylactic Reaction SMQ Broad search as specified in the RISA AAC Charter.

Adverse Event per 100 Patient-Years of Exposure

Adverse events occurring during the analysis period for each population will be presented by event rate per 100 patient-years. These will be presented for any TEAEs, serious adverse events, Areas of Special Interest.

AEs per 100 patient-years of exposure is defined as the number of AEs divided by the total exposure in 100 patient-years. Note that one event per preferred term per day per subject will be counted in the calculation of the number of AEs (i.e., a preferred term will not be counted twice on the same day for the same subject). See the calculation method below.

$$100 \times \frac{\text{Number of TEAEs}}{\text{Total Patient Years}}$$

where total patient years is defined as the sum of the study drug exposure (defined as date of last dose – date of first dose + 140 days (5 half-lives)) of all subjects normalized by 365.25, and rounded to one decimal place.

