6.1.3 Relationship to Study Drug

The investigator will use the following definitions to assess the relationship of the AE to the use of study drug:

Reasonable Possibility	After consideration of factors including timing of the event, biologic plausibility, clinical judgment, and potential alternative causes, there is sufficient evidence (information) to suggest a causal relationship.
No Reasonable Possibility	After consideration of factors including timing of the event, biologic plausibility, clinical judgment, and potential alternative causes, there is insufficient evidence (information) to suggest a causal relationship.

For causality assessments, events assessed as having a reasonable possibility of being related to the study drug will be considered "associated." Events assessed as having no reasonable possibility of being related to study drug will be considered "not associated." In addition, when the investigator has not reported a causality or deemed it not assessable, AbbVie will consider the event associated.

[figure not shown]
If an investigator's opinion of no reasonable possibility of being related to study drug is given, an 'Other' cause of event must be provided by the investigator for the SAE.

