Week 84	589	[548, 631]
Week 96	673	[632, 715]
Week 108	757	[716, 799]
Week 120	841	[800, 883]
Week 132	925	[884, 967]
Week 144	1009	[968, 1051]
Week 156	1093	[1052, 1177]
Week 180	1261	[1178, 1345]
Week 204	1429	[1346, 1513]
Week 228	1597	[1514, 1681]
Week 252	1765	[1682, 1835]

a. If time is collected in vital signs, restrict to records prior to the first dose of RZB in Study M15-997.

Note: Rx Day calculated relative to first dose date of risankizumab.

Table 11. Visit Windows for Analysis of NAPSI, PPASI, PSSI, and DLQI (UST_RZB, FUM_RZB, RZB_Japan Populations)

Window Label	Target Day	Interval
Entry of Study M15-997	1	≤ 1
Week 24	169	[2, 253]
Week 48	337	[254, 421]
Week 72	505	[422, 589]
Week 96	673	[590, 715]
Week 108	757	[716, 799]
Week 120	841	[800, 925]
Week 144	1009	[926, 1051]
Week 156	1093	[1052, 1177]
Week 180	1261	[1178, 1345]
Week 204	1429	[1346, 1513]
Week 228	1597	[1514, 1681]
Week 252	1765	[1682, 1835]

Note: Rx Day calculated relative to first dose date of risankizumab.

Definition of Missing Data Imputation

No global imputation is taking place at the database level. Efficacy related imputations are outlined in Section 10.0. There is no imputation for missing values in the safety analyses.

Rounding of Numeric Results

Rounding will be performed for presentation of results. No rounding will be performed before or during analyses. The ROUND function of SAS will be used to round results.

When dichotomizing continuous variables, associated continuous variables will be rounded to 9 decimal points before applying the cutoff point to determine the response status (for example, percent change from baseline in PASI score will be rounded to 9 decimal places before comparing to 90%).

The mean and median will be rounded for presentation to 1 decimal more than the data entered into the database. The standard deviation will be rounded to 2 decimal places more than the data entered into the database. The minimum and maximum values will be presented as entered into the database.

Probabilities will be rounded to 3 decimal places before assignment of statistical significance and will be presented in rounded format. Probabilities that round to zero or are reported by SAS as zero will be presented as "< 0.001." Probabilities that round to 1 or are reported by SAS as 1 will be presented as "> 0.999."

7.0 Demographics, Baseline Characteristics, Medical History, and Previous/Concomitant Medications

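### Protocol 6.1.3 treats missing causality as associated, but SAP 11.2.1 counts it as unknown, so related-AE and related-SAE counts can fall short of the protocol's rule

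*SAP*

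**What the plan says.** **Protocol 6.1.3 (Relationship to Study Drug).** The investigator rates each AE as having a reasonable possibility, or no reasonable possibility, of being related to study drug; the first counts as associated. For gaps, "when the investigator has not reported a causality or deemed it not assessable, AbbVie will consider the event associated". The sentence is not limited to serious events or to expedited reporting.

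**SAP 11.2.1, Adverse Events by Maximum Relationship.** "Relationship of an AE to study drug is assessed by the investigator and collected in the CRF as 'Yes' or 'No". Then: "If a subject has an adverse event with unknown relationship, the subject will be counted in the relationship category of" *unknown*, even where another occurrence of the same event is rated No. A Yes overrides this: "If the subject has another occurrence of the same adverse event with a relationship assessment of" Yes, the subject goes to the yes category.

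**SAP 11.2.1, Adverse Event Overview.** Two rows concern causality: "Any AE that was assessed as related to study drug by the investigator" and "Any serious AE that was assessed as related to study drug by the investigator". No rule assigns missing relationship to either row.

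**SAP 6.0.** "There is no imputation for missing values in the safety analyses".

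**SAP 14.1.** The heading for changes between the protocol and the SAP has no entry under it in the text available.

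**The concern.** The protocol sets a conservative default for missing causality, and no output described in the SAP applies it. The SAP sets a different default without saying that it departs from the protocol. Elsewhere it does say so: SAP 11.3.2 states that laboratory values will be graded by CTCAE rather than RCTC, and gives the reason.

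The SAP also presumes conservatively in a neighbouring case. An AE with an incomplete onset date is taken as treatment-emergent unless other evidence shows otherwise. Missing causality gets no such presumption, although here the protocol prescribes one.

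Long-term safety is the primary objective, and the related-AE and related-SAE rows sit in the overview table. A reader who knows Protocol 6.1.3 would expect those rows to include events of missing causality. They would not, and nothing in the overview would show how many had been left out.

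**Working it through.** The documents give no figure on this point, so there is nothing to reproduce. The check applies both rules to the same data.

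**Inputs**
- Protocol rule (6.1.3): Yes or missing gives associated; No gives not associated.
- SAP rule (11.2.1): Yes overrides unknown, and unknown overrides No.
- The CRF offers only Yes or No, so unknown in practice means an unanswered field.
- No imputation in safety analyses (SAP 6.0), so a missing value is not set to Yes elsewhere.
- Planned enrolment about 2200 (Protocol 8.2, SAP 4.3), used only for scale.

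**Step 1: every pattern for one or two occurrences of the same event in a subject** (3 single + 6 paired = 9)

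| Occurrences | SAP category | Protocol category | Differ? |
|---|---|---|---|
| Yes | yes | associated | no |
| No | no | not associated | no |
| Unknown | unknown | associated | **yes** |
| Yes, Yes | yes | associated | no |
| Yes, No | yes | associated | no |
| Yes, Unknown | yes | associated | no |
| No, No | no | not associated | no |
| No, Unknown | unknown | associated | **yes** |
| Unknown, Unknown | unknown | associated | **yes** |

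The rules differ in 3 of 9 patterns, each with an unknown and no Yes. In all three the SAP leaves the subject out of the related count and the protocol's rule puts the subject in. No pattern runs the other way.

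**Step 2: where a reader could see the difference.** The maximum-relationship table is planned for treatment-emergent AEs and carries an unknown category, so a reader can add it to yes. The overview rows have no such line. For serious events, SAP 11.2.1 describes only a table by system organ class and preferred term and a by-subject listing. Among the summary tables described there, the overview row is the only one specific to related SAEs. The full table list is in a separate document (SAP 17.0), so this holds for the SAP text alone.

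**Step 3: size.** These tables count subjects, not events. For the overview AE row:

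shortfall = number of subjects with at least one AE of missing relationship and no AE rated Yes.

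A subject with a missing relationship on one AE and a Yes on another is already in the row, so missing events do not convert one for one. If q is the share of subjects in the shortfall group, the shortfall is 2200 × q. The documents do not give q; the values below are assumptions.

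| q | 2200 × q | Change in percentage points |
|---|---|---|
| 0 | 0 | 0 |
| 0.1% | 2.2 | 0.1 |
| 0.5% | 11 | 0.5 |
| 1% | 22 | 1.0 |
| 2% | 44 | 2.0 |

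The related-SAE row follows the same formula, restricted to serious AEs.

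**Step 4: what does not move.** Counts of any AE and any serious AE, and the rates per 100 patient-years for TEAEs, serious AEs and areas of interest, do not use relationship.

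**The case against.** The strongest answer is that the two rules describe different assessors. Protocol 6.1.3 states the sponsor's view when the investigator is silent; the SAP rows and the relationship table are labelled as the investigator's assessment. An AE the investigator never rated was not rated as related by the investigator, so the rows are accurate as worded. The protocol sentence also stands among the AE definitions rather than in the safety analysis section (8.1.5), which asks for no related-AE table, and Protocol 8.1 leaves analysis detail to the SAP.

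This reading is plausible, and part of it stands: events cannot be added to rows labelled as investigator-assessed without changing the label. It does not remove the conflict. Neither document says that the sponsor's and the investigator's causality are to be reported separately, and no output described in the SAP uses the sponsor's rule.

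A second answer is that missing causality may be rare or absent. The CRF field is Yes or No, Protocol 6.1 requires the investigator to record relationship for each AE, and Protocol 10.2 has eCRFs reviewed for completeness. This stands in full. A reader might infer that drug-related AEs *are* under-counted; the documents support only that they *can* be.

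A reader might also infer that the preceding studies, run by two sponsors, bring in many events without causality. The SAP does integrate their data, but neither document says how completely causality was recorded there, or that this protocol's rule extends to it.

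Finally, the SAP rule is not lenient throughout: unknown overrides No, and the relationship table shows the unknown category openly. That is true of that table but does not help the overview rows.

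**Conclusion.** The inconsistency is real and undeclared, and its direction is certain: relative to Protocol 6.1.3, the SAP's related-AE and related-SAE counts can match or be too low, never too high. Its size is unknown and may be zero. The 0 to 44 subjects (0 to 2.0 percentage points of about 2200) rests wholly on an assumed share of 0 to 2% and on planned enrolment; it illustrates scale and is not an estimate.

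This is a minor point. The study is descriptive with no statistical test, the main AE, SAE and exposure-adjusted summaries are untouched, and the relationship table lets a careful reader recover the unknown group. It is worth settling because the overview rows conceal any missing causality.

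**What to change.** In SAP 11.2.1:
- Count missing or not-assessable relationship as related in the maximum-relationship table and in both overview rows. The same sentence should cover the summary of causally related AEs announced under the system organ class tables.
- Relabel the rows, for example: assessed as related by the investigator, or relationship missing.
- Footnote the number of subjects so classified, for AEs and serious AEs separately.
- State whether the rule applies to AEs carried over from the preceding studies.

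In SAP 6.0, add this as an exception to the statement that safety analyses use no imputation.

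If the sponsor prefers rows showing the investigator's view alone, the minimum is to record and justify the departure in SAP 14.1 and report the number with missing relationship beside the overview rows.

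The cost is a few sentences, a changed label and a footnote. No new data are needed. The related counts stay the same or rise, in the direction the protocol already prescribes. The change belongs in the SAP before database lock.
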